6.1.1 Relative Dose Intensity (%)

RDI (%) =
$$100\% * \frac{Actual\ Dose\ Intensity\ (ADI)}{Planned\ Dose\ Intensity\ (PDI)}$$

Where ADI and PDI are defined below:

6.1.1.1 Dose Calculations

•
$$PDI\left(\frac{mg}{day}\right) = \frac{\sum_{j=1}^{m} Planned\ Dose\ (mg)_{j}}{\sum_{j=1}^{m-1} Planned\ Cycle\ Length\ (days)_{j} + Last\ Cycle\ Length\ (days)_{j}}$$

[Note: Planned Dose is the initial per-protocol dose assigned to the participant.]

•
$$ADI\left(\frac{mg}{day}\right) = \frac{\sum_{j=1}^{m} Actual \ Dose \ (mg)_{j}}{\sum_{j=1}^{m} Actual \ Cycle \ Length \ (days)_{j}}$$

Where j = 1, 2, 3, m are the indices for the cycle, and the cycle length is defined as follows:

Except for last cycle,;

$$Cycle\ Length\ (days) = 28$$

Since participants may discontinue the study treatment at any time, the last cycle may not be a complete cycle of treatment, therefore it needs special attention.

Last Cycle Length (days) = (min [Date of Last AC699 Dose, Date of Death, Date of Data Cut-off] - Date of First AC699 Dose in Last Cycle + 1)

6.2 Adverse Events

A TEAE is defined as an AE with an onset or worsening grade on or after the first dose of study treatment up to 30 days after the end of treatment or up to the start of other anticancer

therapy (which occurs earlier). AEs will be graded using the National Cancer Institute - Common Terminology Criteria for Adverse Events (CTCAE) version 5.0 where applicable and coded using MedDRA version 25.0 or higher.

An overall summary of on treatment AEs will present the frequency and percentage of participants by the following categories:

- Any TEAEs
- Any AC699-related TEAEs
- Any grade ≥3 TEAE
- Any AC699-related grade ≥3 TEAE
- Any TEAE leading to death
- Any AC699-related TEAE leading to death
- Any treatment-emergent serious adverse events (SAE)
- Any AC699-related treatment-emergent SAEs
- Any TEAE leading to discontinuation of AC699
- Any TEAE leading to interruption of AC699
- Any TEAE leading to reduction of AC699

Additional summaries for all of the above categories, will present the frequency and percentage of participants experiencing at least one event by MedDRA SOC and MedDRA preferred term (PT).

Additional summaries for the following categories will present the frequency and percentage of participants experiencing at least one event by MedDRA SOC, MedDRA PT, and worst CTCAE grade:

- Any TEAEs
- Any AC699-related TEAEs

Specific listings, with all relevant information, will be provided for TEAEs, SAEs, TEAEs with an outcome of death, and TEAEs leading to discontinuation of AC699.

6.3 **Participant Deaths**

Death and primary cause of death will be summarized by frequency and percentage.

All death data will be provided in listings.

6.4 **Laboratory Parameters**

Descriptive statistics for each lab parameter (chemistry, hematology, urinalysis, and coagulation) at baseline, each scheduled post-baseline assessment, and changes from baseline to scheduled post-baseline assessments will be presented.

Abnormal laboratory values will be graded according to CTCAE version 5.0, if applicable. Clinical descriptions will not be considered when grading; grading will only be based on numeric results and thresholds.

A shift table will be presented for each laboratory parameter to display the shift from baseline to the maximum post-baseline CTCAE grade within 30 days post-treatment, inclusive of unscheduled post-baseline assessments. For parameters that can be graded in either direction

(both high and low), the shift in both directions will be presented. For parameters that cannot be graded per CTCAE, shift tables based on the normal ranges will be presented for both the minimum and maximum values within 30 days post-treatment. Normal lab ranges will be based on local lab ranges.

A listing of potential Hy's Law cases will be provided (defined as alanine or aspartate aminotransferase $> 3 \times$ upper limit of normal with concurrent total bilirubin $> 2 \times$ upper limit of normal without findings of cholestasis [alkaline phosphatase $< 2 \times$ upper limit of normal]).

All lab data will be provided in listings. Urinalysis will not be summarized and only listed.

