2. STUDY OBJECTIVES AND ENDPOINTS

Table 1 Study Objectives and Corresponding Endpoints

Primary Objective:	Endpoint/Variable:
Evaluate the safety and tolerability of AC699	Incidence and severity of dose-limiting toxicities (DLTs), treatment-emergent adverse events (TEAEs), and clinically significant Grade 3 or higher laboratory abnormalities
Secondary Objectives:	Endpoint/Variable:
Evaluate the preliminary anti-tumor activity of AC699	Objective response rate (ORR [CR+PR]) as defined by Response Evaluation Criteria in Solid Tumors (RECIST) Version 1.1, clinical benefit rate (CBR) (complete response [CR]+partial response [PR]+stable disease [SD] \geq 24 weeks), duration of response (DOR), disease control rate (DCR), and progression-free survival (PFS)
Characterize the pharmacokinetic (PK) profile of a single dose and after multiple doses of AC699	PK parameters
Exploratory Objectives:	Endpoint/Variable:
Evaluate the pharmacodynamic (PDx) effect of AC699 in ER α degradation	Change of ER α expression in tumors from baseline to post-treatment if tumor tissue is available from paired biopsies
Evaluate the relationship between circulating tumor cells (CTCs) count and administration of AC699	Correlation between CTC count at baseline and post-treatment, and anti-tumor activity (ORR, CBR, DOR, DCR, and PFS)
Evaluate the relationship between estrogen receptor gene 1 (ESR1) mutation status and antitumor activity of AC699	Correlation between ESR1 mutational status and anti-tumor activity (ORR, CBR, DOR, DCR, and PFS)
Evaluate the relationship between circulating tumor DNA (ctDNA) levels and anti-tumor activity of AC699	Correlation between ctDNA levels at baseline & post-treatment and anti-tumor activity (ORR, CBR, DOR, DCR, and PFS)

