5.2 End of Study Treatment (EOT)

Patients will be discontinued from study treatment for any of the following reasons:

- Objective disease progression (Patients who are receiving clinical benefit in the opinion of the treating Investigator may be allowed to stay on study treatment after consultation with the Medical Monitor and Sponsor Representative)
- Intolerable toxicity that are irreversible thought to be related to study drug
- Treatment discontinuation criteria as per Dose Modification criteria (See Section 6)
- Conditions requiring therapeutic intervention not permitted by the protocol
- Intercurrent illness interfering with the patient's ability to follow study requirements (treatment or assessments); this will be at the Investigator's discretion

CONFIDENTIAL

Study Drug: AC699 Sponsor/Development Innovations Study Numbers: AC699-001/BRE 401

- Another condition leading to patient's inability to comply with study requirements
- Patient lost to follow-up
- Patient withdraws consent from study treatment or study participation altogether
- Start of a new anti-cancer therapy
- Patient's death
- Patient's participation in the study is terminated by Investigator
- Study termination

After discontinuation from protocol treatment, patients must be followed for AEs for 30 days after their last dose of study drug. Patients discontinuing study treatment prior to disease progression (per RECIST v1.1) will go on to extended follow-up. During extended follow-up response assessments will be performed as described in Section 7.4.3. All new AEs occurring during the 30-days following termination of treatment must be reported and followed until resolution or stabilization unless, in the opinion of the Investigator, these values are not likely to improve because of the underlying disease. In this case, the Investigator must record his or her reasoning for this decision in the patient's medical records and indicate that the outcome is not resolved on the AE pages of the electronic case report form (eCRF).

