7.4.2 Thirty-Day Safety Follow-up

All patients will be followed during the off-treatment period until all treatment-related toxicity resolves, or 30 days (\pm 5 days) post-study drug discontinuation, or until the start of another anticancer treatment. Any concomitant medications received up to 30 days after the last dose of study drug should be recorded.

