10.4.3 Safety Analysis

Safety will be assessed through the analysis of the reported incidence of treatment-emergent AEs. Treatment-emergent AEs are those with an onset on or after the initiation of therapy and will be graded according to NCI CTCAE Version 5.0.

The AEs will be coded using the current version of Medical Dictionary for Regulatory Activities (MedDRA; https://www.meddra.org/about-meddra/) and summarized using system organ class and preferred term by dose level for all patients in the Safety set/population. In addition, summaries of SAEs, AEs leading to treatment discontinuation, AEs by maximum NCI CTCAE grade, and AEs related to study treatment will also be presented by dose level.

Other safety endpoints, including laboratory results, vital signs, and ECG findings, will be summarized for all patients in the Safety set.

Concomitant medications will be coded using the World Health Organization Drug Dictionary (WHO DD; https://www.who-umc.org/), and they will be listed and summarized by dose level.

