All SAEs regardless of causality and reported during the above-mentioned reporting period, should be followed until resolution, stabilization, or start of a new anticancer therapy, whichever is first; unless, in the opinion of the Investigator, the event is not likely to improve because of the underlying disease. In this case, the Investigator must record his or her reasoning for this decision in the patient's medical record.

All other AEs reported during the above-mentioned reporting period will be followed until resolution or through the 30-days safety follow-up period, or start of a new anticancer therapy, whichever is first.

CONFIDENTIAL

Sponsor/Development Innovations Study Numbers: AC699-001/BRE 401

Final Protocol: 07 May 2024 Version 4.0

Thirty days after completion of protocol-specific treatment or discontinuation, only AEs, SAEs, or deaths assessed by the Investigator as treatment-related are to be reported.

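### The TEAE window closes at the next anticancer therapy but the laboratory shift-table window does not, and late AC699-related events are counted in none of the SAP 6.2 summaries

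*SAP*

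**What the plan says.** The primary endpoint (protocol Section 2) is "Incidence and severity of dose-limiting toxicities (DLTs), treatment-emergent adverse events (TEAEs), and clinically significant Grade 3 or higher laboratory abnormalities".

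**TEAEs.** SAP 6.2 counts onset or worsening from the first dose "up to 30 days after the end of treatment or up to the start of other anticancer" "therapy (which occurs earlier"). Protocol 10.4.3 sets no end: "Treatment-emergent AEs are those with an onset on or after the initiation of therapy". SAP Section 8 declares no change from the protocol.

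**Laboratory values.** The SAP 6.4 graded shift table uses "the maximum post-baseline CTCAE grade within 30 days post-treatment, inclusive of unscheduled post-baseline assessments". Parameters without a CTCAE grade get a normal-range shift table over the same 30 days. Neither table mentions the next therapy.

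**Safety follow-up in the protocol.**
- Section 5.2: "patients must be followed for AEs for 30 days after their last dose of study drug". Section 11.1.5, Section 11.2 and the AE row of the Schedule of Assessments also give 30 days with no exception.
- Section 7.4.2 names three end points, the last being "or until the start of another anticancer treatment". Schedule footnote p does the same. Section 5.3 ends study participation when a new cancer treatment starts.
- After day 30, Section 11.1.5 says "only AEs, SAEs, or deaths assessed by the Investigator as treatment-related are to be reported".

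**The concern.** TEAEs and Grade 3 or higher laboratory abnormalities sit side by side in one primary endpoint, yet their summaries treat the next cancer drug in opposite ways. A neutropenia caused by chemotherapy begun inside the 30 days is outside the TEAE tables but inside the laboratory shift table. SAP 6.4 grades on numeric results alone, so no attribution step removes it.

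The AE tables have the reverse problem. The protocol has sites report events they attribute to AC699 even after day 30, but the SAP has no incidence summary that can hold them. In a first-in-human trial, delayed toxicity attributed to the drug should be visible in a table.

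**Working it through.** The plan gives no figure to reproduce here. The check sets the rules side by side, followed by short arithmetic.

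**1. Windows**

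| Rule | End of window | Cut at next therapy? |
|---|---|---|
| SAP 6.2 TEAE summaries | Earlier of 30 days and next therapy | Yes |
| SAP 6.4 CTCAE shift table | 30 days post-treatment | No |
| SAP 6.4 normal-range shift table | 30 days post-treatment | No |
| SAP 6.3 death summary | None stated | No |
| Protocol 10.4.3 TEAE definition | None stated | No |
| DLT (protocol 5.1) | First 28 days on treatment | Not relevant |

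**2. Length of the mismatch.** Let s be the day after the last dose on which the next therapy starts, with s ≤ 30. The TEAE window then runs s days and the laboratory window 30, so laboratory-only days = 30 − s:
- s = 7: 23 days
- s = 14: 16 days
- s = 21: 9 days
- s = 28: 2 days

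Under a common cut the mismatch is 0 for every s. The documents do not give s; these values are assumed.

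**3. Which blood draws can fall in the gap.** The EOT visit is preferably within 7 days and at most 14 days after the last treatment, so it will often precede the switch. The 30-day visit includes safety laboratories and has a ±5-day window, that is days 25 to 35. A draw on days 31 to 35 is already outside the SAP 6.4 window. That usually leaves one scheduled draw plus unscheduled tests. Protocol 5.2 adds a source of repeat tests: patients who stop with a Grade 3 or 4 laboratory value are followed until Grade 1 or 2, with no stop at new therapy.

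**4. Whether those draws happen.** Under Sections 5.2, 11.1.5 and 11.2 and the Schedule's AE row, safety collection continues to day 30. Under 5.3, 7.4.2 and footnote p it may stop at the switch. Nothing says which governs. Follow-up of SAEs already reported is also stated three ways: 11.1.5 allows it to stop at new therapy, 11.2 runs it to resolution, and footnote j to resolution or stabilisation.

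**5. Tracing late AC699-related events.** Suppose the next therapy starts on day 14 and an event attributed to AC699 begins on day 20. Section 11.1.5 collects it. Under SAP 6.2 it is not a TEAE, and all 11 overview categories are limited to treatment-emergent events, as are the SOC/PT and worst-grade tables built on them. The event is counted in none. The same holds for a related event beginning on day 40. It still reaches the following places:
- a death is in the SAP 6.3 summary, by primary cause but not by relatedness;
- an SAE is in the SAE listing, which is not restricted to TEAEs;
- anything else is covered only by the general statement in SAP 6 that all safety data are listed.

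**6. Scale in an expanded dose level (n = 20).** One patient is 1/20 = 5 percentage points. Let f be the assumed share of patients with a draw in the 30 days after starting the next therapy, and g the assumed chance that the draw adds a new Grade 3 or higher value. Expected extra patients = n × f × g:
- f = 0.1, g = 0.05: 20 × 0.1 × 0.05 = 0.1 patients (0.5 points)
- f = 0.3, g = 0.15: 20 × 0.3 × 0.15 = 0.9 patients (4.5 points); chance of at least one = 1 − (1 − 0.045)^20 = 0.60
- f = 0.6, g = 0.30: 20 × 0.6 × 0.30 = 3.6 patients (18 points)

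Neither f nor g is in the documents. The range shows only that the effect could be negligible or visible.

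**The case against.** The strongest case against is that this is a harmonisation point with little effect.

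- **The shift table is not the primary endpoint.** The endpoint concerns clinically significant abnormalities; the shift table covers all grades on numeric thresholds and assigns no cause. Values that need action, cause symptoms or are judged adverse become AEs under protocol 11.3.3 and then pass through SAP 6.2, which has the cut. This stands: the SAP names no table for the laboratory component, so the shift table is only its closest graded summary.
- **There may be few values to contaminate.** If sites stop at the switch, as 5.3, 7.4.2 and footnote p allow, little is drawn afterwards. This stands as a limit on size. It also means that data capture may differ between sites, which analysis cannot repair.
- **The protocol conflict is narrower than it looks.** Section 11.1.5 separates collecting new AEs from following those already reported, and these two rules can coexist. That explains part of the difference. It does not settle 5.3, 7.4.2 and footnote p against 5.2 and 11.2, or the three SAE follow-up rules.

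A reader might infer more than the documents support:
- *That late AC699-related events vanish from every SAP output.* They do not: SAP 6.3 summarises all deaths, and SAEs and all safety data are listed.
- *That dose escalation is affected.* DLTs use a fixed window of the first 28 days.
- *That the 14-day washout at entry indicates the gap to the next therapy.* It concerns treatment before AC699 and says nothing about the gap afterwards.

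**Conclusion.** The point holds on the text. The TEAE and laboratory windows differ by 30 − s days for any patient who switches on day s, and the SAP gives no reason. Where blood is drawn in that interval, next-line toxicity can be shown under an AC699 dose level. AC699-related events that begin after the TEAE window are collected but have no incidence summary, apart from deaths in SAP 6.3. The narrowing from protocol 10.4.3 is undeclared. The 30-day limit itself has support in the protocol's AE collection period, so the next-therapy cut is the part that most needs recording.

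The consequence is possible rather than shown. It depends on how many patients switch within 30 days, when they switch, and which follow-up rule sites apply; the documents give none of these. The case for acting now is that correction costs little and that inconsistent collection cannot be put right after database lock.

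**What to change.** 1. **SAP 6.4:** end both shift-table windows at the earlier of 30 days post-treatment and the start of other anticancer therapy. Use the subsequent-therapy date already defined in SAP Table 2, and flag later values in the laboratory listing.
2. **SAP 6.2:** keep the TEAE tables as defined. Add a separate summary of AC699-related AEs, SAEs and deaths with onset after the TEAE window. Adding these events to the existing related-TEAE rows would not work, because a patient could then have a related TEAE and no TEAE.
3. **Protocol:** reconcile 5.3, 7.4.2 and footnote p with 5.2, 11.1.5 and 11.2, and reconcile the SAE follow-up statements in 11.1.5, 11.2 and footnote j, so that all sites collect over the same period.
4. **SAP Section 8:** record the next-therapy cut as a change from protocol 10.4.3.

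The cost is SAP wording, a protocol clarification, minor programming and one more table. The change to the analysis windows needs no new assessments.

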- 8. Patients must have received at least 2 prior endocrine regimens in any setting (neoadjuvant, adjuvant or advanced/metastatic) or at least 1 prior line of endocrine therapy if combined with CDK4/6 inhibitor
- 9. Prior chemotherapy is not required, but up to 3 prior regimens of cytotoxic chemotherapy will be allowed in the locally advanced/ metastatic setting
- 10. Patients must have at least 1 measurable lesion according to Response Evaluation Criteria in Solid Tumors (RECIST) Version 1.1 (Appendix B) or at least 1 predominantly lytic bone lesion in the absence of measurable disease
- 11. Acceptable organ function, as evidenced by the following laboratory data:
 - Renal function, as follows:
 - o Creatinine clearance of ≥60 mL/min by the Cockcroft-Gault equation or equivalent

Study Drug: AC699 Sponsor/Development Innovations Study Numbers: AC699-001/BRE 401

- Liver function as follows:
 - Total bilirubin \leq 1.5 × ULN (\leq 5 × ULN for patients with known Gilbert's syndrome)
 - o Aspartate aminotransferase (AST) ≤2.5 × ULN or ≤5 × ULN in the presence of liver metastases
 - o Alanine aminotransferase (ALT) ≤2.5 × ULN or ≤5 × ULN in the presence of liver metastases
- International normalized ratio (INR) ≤2
- 12. Acceptable hematologic function:
 - Hemoglobin ≥9 g/dL
 - Absolute neutrophil count (ANC) ≥1,000 cells/mm³
 - Platelet count \geq 75,000 cells/mm³
- 13. Male patients with female partners of childbearing potential are required to use two forms of acceptable contraception (Appendix C), including one barrier method, during their participation in the study and for 90 days following last dose. Male patients must also refrain from donating sperm during their participation in the study and for 90 days following last dose.
- 14. Life expectancy ≥12 weeks after the start of the treatment according to the Investigator's judgment.
- 15. Backfill patient must have historical testing available to confirm ESR1 mutations and must meet all inclusion criteria listed here.

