6.2.1 Specific Recommendations for Liver Function Test Abnormalities

For patients with Grade 3 liver enzyme elevations (AST/ALT), AC699 should be held until the values recover to \leq Grade 1 or baseline. Patients with an elevation of AST/ALT \geq 3 × ULN in conjunction with a bilirubin \geq 2 × ULN may remain in the study if a correctable, non-drug related cause of the liver test evaluations can be documented; otherwise, the patient must be discontinued from the study.

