Appendix E: Hy's Law

Reference: FDA Guidance for Industry (issued July 2009) "Drug-induced liver injury: Premarketing clinical evaluation"

Introduction

This Appendix describes the process to be followed in order to identify and appropriately report cases of Hy's Law (HL). It is not intended to be a comprehensive guide to the management of elevated liver biochemistries.

During the course of the study, the Investigator will remain vigilant for increases in liver biochemistry. The Investigator is responsible for determining whether a subject meets potential Hy's Law (PHL) criteria at any point during the study.

The Investigator participates, together with Accutar Biotechnology, Inc. clinical project representatives, in review and assessment of cases meeting PHL criteria to agree whether HL criteria are met. Hy's Law criteria are met if there is no alternative explanation for the elevations in liver biochemistry other than drug-induced liver injury (DILI) caused by the investigational medicinal product.

The Investigator is responsible for recording data pertaining to PHL/HL cases and for reporting AEs and SAEs according to the outcome of the review and assessment in line with standard safety reporting processes.

Definitions

Potential Hy's Law (PHL)

Aspartate aminotransferase (AST) or alanine aminotransferase (ALT) $\ge 3 \times$ upper limit of normal (ULN) together with total bilirubin (TBL) $\ge 2 \times$ ULN at any point during the study following the start of study medication irrespective of an increase in alkaline phosphatase (ALP).

Hy's Law (HL)

Aspartate aminotransferase or ALT \geq 3 × ULN together with TBL \geq 2 × ULN, where no other reason other than the investigational product can be found to explain the combination of increases, e.g., elevated ALP indicating cholestasis, viral hepatitis, another drug.

For PHL and HL the elevation in transaminases must precede or be coincident with (i.e., on the same day) the elevation in TBL, but there is no specified time frame within which the elevations in transaminases and TBL must occur.

Identification of potential Hy's Law cases

In order to identify cases of PHL it is important to perform a comprehensive review of laboratory data for any subject who meets any of the following identification criteria in isolation or in combination:

- AST $>3 \times ULN$
- ALT >3 × ULN
- TBL \geq 2 × ULN

Study Drug: AC699

CONFIDENTIAL

Sponsor/Development Innovations Study Numbers: AC699-001/BRE 401

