- If at any time (in consultation with the Medical Monitor) the PHL case meets serious criteria, report it as an SAE using standard reporting procedures.

CONFIDENTIAL

Sponsor/Development Innovations Study Numbers: AC699-001/BRE 401

Final Protocol: 07 May 2024 Version 4.0

Review and assessment of potential Hy's Law cases

The instructions in this section should be followed for all cases where PHL criteria are met.

No later than 3 weeks after the biochemistry abnormality was initially detected, the Investigator contacts the Medical Monitor in order to review available data and agree on whether there is an alternative explanation for meeting PHL criteria other than DILI caused by the investigational product. The Accutar Biotechnology, Inc. Clinical Lead or equivalent and Medical Monitor will also be involved in this review together with other subject-matter experts as appropriate.

According to the outcome of the review and assessment, the Investigator will follow the instructions below.

If there is an agreed alternative explanation for the ALT or AST and TBL elevations, a determination of whether the alternative explanation is an AE will be made and subsequently whether the AE meets the criteria for a SAE:

- If the alternative explanation is not an AE, record the alternative explanation on the appropriate eCRF.
- If the alternative explanation is an AE/SAE, record the AE/SAE in the eCRF accordingly and follow the reporting standard practices.

If it is agreed that there is no explanation that would explain the ALT or AST and TBL elevations other than the investigational product:

Report an SAE (report term Hy's Law) according to the Sponsor's standard processes.

- The 'Medically Important' serious criterion should be used if no other serious criteria apply.
- As there is no alternative explanation for the HL case, a causality assessment of 'related' should be assigned.

If there is an unavoidable delay of over 3 weeks in obtaining the information necessary to assess whether or not the case meets the criteria for HL, then it is assumed that there is no alternative explanation until such time as an informed decision can be made:

- Report an SAE (report term Potential Hy's Law) applying serious criteria and causality assessment as per above.
- Continue follow-up and review according to the agreed plan. Once the necessary
 supplementary information is obtained, repeat the review and assessment to determine

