 whether HL criteria are met. Update the SAE report according to the outcome of the
 review amending the reported term if an alternative explanation for the liver biochemistry
 elevations is determined.

Actions required when potential Hy's Law criteria are met before and after starting study treatment

This section is applicable to subjects with liver metastases who meet PHL criteria on study treatment having previously met PHL criteria at a study visit prior to starting study treatment.

At the first on-study treatment occurrence of PHL criteria being met, the Investigator will determine if there has been a significant change in the subjects' condition compared with the last visit where PHL criteria were met.

CONFIDENTIAL

Sponsor/Development Innovations Study Numbers: AC699-001/BRE 401

Final Protocol: 07 May 2024 Version 4.0

- If there is no significant change, no action is required.
- If there is a significant change, notify the Sponsor's representative.

A "significant" change in the subject's condition refers to a clinically relevant change in any of the individual liver biochemistry parameters (ALT, AST, or TBL) in isolation or in combination, or a clinically relevant change in associated symptoms. The determination of whether there has been a significant change will be at the discretion of the Investigator, this may be in consultation with the Medical Monitor if there is any uncertainty.

Actions required for repeat episodes of potential Hy's Law

This section is applicable when a subject meets PHL criteria on study treatment, and has already met PHL criteria at a previous on-study treatment visit.

The requirement to conduct follow-up, review, and assessment of a repeat occurrence(s) of PHL is based on the nature of the alternative cause identified for the previous occurrence.

The Investigator should determine the cause for the previous occurrence of PHL criteria being met and answer the following question:

Was the alternative cause for the previous occurrence of PHL criteria being met found to be the disease under study (e.g., chronic or progressing malignant disease, severe infection, or liver disease), or did the subject meet PHL criteria prior to starting study treatment and at first onstudy treatment visit, as described in "Actions required when potential Hy's Law criteria are met before and after starting study treatment".

- If No: Follow the process described in "Potential Hy's Law criteria not met".

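### The SAP 6.4 listing of potential Hy's Law cases is narrower than the protocol's Appendix E definition of that term and can omit cases the protocol requires to be reviewed

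*SAP*

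**What the plan says.** **SAP 6.4 (Laboratory Parameters)** promises a listing of potential Hy's Law cases. Entry requires ALT or AST > 3 × the "upper limit of normal with concurrent total bilirubin" > 2 × ULN, without cholestasis, which is expressed as ALP < 2 × ULN. The SAP does not define *concurrent*, and it sets no time limit on the listing.

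**Protocol Appendix E (Definitions)** defines the term Potential Hy's Law (PHL) for the whole period after study medication starts: AST or ALT ≥ 3 × ULN together with total bilirubin (TBL) ≥ 2 × ULN, "irrespective of an increase in alkaline phosphatase (ALP". The transaminase rise must come before, or on the same day as, the bilirubin rise, but "there is no specified time frame within which the elevations in transaminases and TBL must occur". Raised ALP enters only at the next step, as one possible other explanation when deciding whether a PHL case is Hy's Law. On review, Appendix E says: "The instructions in this section should be followed for all cases where PHL criteria are met".

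**Protocol 6.2.1** also uses ≥ 3 × and ≥ 2 × ULN with no ALP condition. Such patients "may remain in the study if a correctable, non-drug related cause of the liver test evaluations can be documented".

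**Protocol 5.1 (Dose-Limiting Toxicity)** has a bullet almost identical to the SAP wording: > 3 ×, concurrent > 2 ×, no cholestasis (ALP > 2 × ULN). It applies to the first 28 days and itself refers to Appendix E.

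**SAP section 8** declares no change from the analyses in the protocol.

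**The concern.** The SAP uses the protocol's name for a set of patients but applies a smaller set's rule. It moves the cholestasis judgement, which Appendix E leaves to case review, into the entry filter, and an ALP cut-off cannot say why ALP is raised.

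The consequence is a possible contradiction within the study report. If review finds no cause other than the drug, Appendix E requires an SAE termed Hy's Law, assessed as related. If the necessary information is unavoidably delayed beyond 3 weeks, "then it is assumed that there is no alternative explanation until such time as an informed decision can be made", and the SAE is reported as Potential Hy's Law, again as related. Either patient could be missing from the listing that carries that name. The SAP 6.4 shift tables would not reveal the omission, because they show one parameter at a time and this signal is a combination of two. Safety is the primary objective of this first-in-human study.

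**Working it through.** No sample size or error rate is involved. The check sets the two rules side by side and applies them to illustrative laboratory patterns.

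**Rules.** AT is the higher of AST and ALT; AT, TBL and ALP are in multiples of ULN; lag is the day of the TBL rise minus the day of the AT rise.
- Appendix E: AT ≥ 3, TBL ≥ 2, lag ≥ 0, any ALP.
- SAP 6.4: AT > 3, TBL > 2, ALP < 2, and lag within the meaning of *concurrent*. Two meanings were tried, both assumptions: same day, and within 14 days either way.

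| AT | TBL | ALP | Lag (days) | Appendix E | SAP, same day | SAP, ±14 days |
|---|---|---|---|---|---|---|
| 5 | 3 | 1 | 0 | yes | yes | yes |
| 5 | 3 | 2 | 0 | yes | no | no |
| 5 | 3 | 3 | 0 | yes | no | no |
| 5 | 3 | 1 | 14 | yes | no | yes |
| 5 | 3 | 1 | 28 | yes | no | no |
| 5 | 3 | 3 | 14 | yes | no | no |
| 3 | 3 | 1 | 0 | yes | no | no |
| 5 | 2 | 1 | 0 | yes | no | no |
| 5 | 3 | 1 | −14 | no | no | yes |

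Appendix E takes 8 of the 9 patterns. The SAP rule takes 1 (same day) or 3 (±14 days). These counts show the logic only; they are not expected patient numbers.

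**What does not depend on the reading.** The rows with ALP 2 or 3, and the rows with AT exactly 3 or TBL exactly 2, fail the SAP rule in both columns.

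**What does.** The 14-day lag with normal ALP is lost under the same-day reading and kept under the 14-day one. The 28-day lag is lost under both. In general, the listing loses every lag longer than *concurrent* allows. If the word means same draw, it loses every different-day case.

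**Can ALP be high at entry?** Inclusion criterion 11 (protocol 3.1) limits bilirubin, AST, ALT and INR, but not ALP. Take a patient whose ALP is 2.6 × ULN at baseline and stays there. A new ALT of 8 × and bilirubin of 3 × ULN on Day 29 meets Appendix E, yet this patient can never enter the SAP listing.

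**Can the other tests be high at entry?** The limits are 2.5 × ULN for AST and ALT (5 × with liver metastases) and 1.5 × ULN for bilirubin (5 × with Gilbert's syndrome). Since 5 ≥ 3 and 5 ≥ 2, one Appendix E threshold can be met at entry with either condition, and both thresholds only with the two conditions together. Appendix E has separate instructions for patients with liver metastases "having previously met PHL criteria at a study visit prior to starting study treatment", so a wider listing should mark pre-treatment elevations.

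**Is the present set contained in the wider one?** Under a same-draw reading, yes: AT > 3 and TBL > 2 on one draw satisfy AT ≥ 3, TBL ≥ 2 and lag 0. Under a ±14-day reading, no: the last row, bilirubin first, is in the SAP set but is not PHL under Appendix E.

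**The case against.** The strongest reply is that the mismatch begins in the protocol. The DLT bullet cites Appendix E while giving the narrower rule, and the SAP follows that bullet. A more specific listing is a defensible choice, since Appendix E itself names cholestasis as another explanation. This stands in part: a reader might infer that the SAP simply contradicts the protocol, but the protocol holds both wordings. It does not rescue the listing, which runs beyond the 28-day DLT period under the Appendix E name. Nor does the SAP's age explain the difference. It still carries the older figures of 15 patients per dose level and 60 in total, but the change summaries for protocol versions 3.0 and 4.0 show no change to Appendix E.

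Three stronger readings are tempting, and the documents do not support them:

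- *All sequential cases are lost.* That requires *concurrent* to mean same draw. Nor does the visit schedule guarantee long gaps between draws: the end-of-treatment visit includes safety laboratory tests, preferably within 7 days of last treatment, and Appendix E requires a repeat draw when its identification criteria are met in a local laboratory.
- *Bone disease makes raised ALP common here.* Inclusion criterion 10 admits patients with "at least 1 predominantly lytic bone lesion in the absence of measurable disease", but the documents give no ALP distribution and do not link such lesions to ALP. Only the missing entry limit is documented.
- *Liver cases escape safety review.* Appendix E review is carried out by the investigator, the Medical Monitor and the sponsor's clinical lead, and does not use this listing.

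It also stands that other outputs hold the data: the SAE listing (SAP 6.2), the full laboratory listings (SAP 6.4) and the liver-assessment listing (SAP 6.9). The last is probably fed by the liver eCRF modules completed for PHL cases, although the documents do not say so.

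**Conclusion.** The point holds and is minor. As written, the listing does not contain all the cases its name denotes in the protocol. Two omissions are certain from the text: Appendix E cases with ALP ≥ 2 × ULN at the qualifying draws, and cases exactly at 3 × or 2 × ULN. The loss of sequential cases is conditional on how *concurrent* is read, and only lags beyond that meaning are lost.

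The documents give no rate for any of these cases, so the number omitted cannot be estimated. The defect is an incomplete named safety display, not lost data: no estimate, dose decision or patient-management step rests on it. The conclusion assumes that the listing is meant to show Potential Hy's Law as Appendix E uses the term, which its name suggests and SAP section 8 does not disclaim.

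**What to change.** In SAP 6.4, list every patient who, after first dose, has AST or ALT ≥ 3 × ULN on or before a day with total bilirubin ≥ 2 × ULN, at any interval and whatever the ALP. Show dates and values of AST, ALT, bilirubin and ALP, with flags for:

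- elevation of both on the same day;
- ALP ≥ 2 × ULN;
- PHL criteria already met, or liver tests (including ALP) already raised, before treatment.

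If *concurrent* was meant as same draw, the present set can be recovered from the flags and values. If a wider window was meant, bilirubin-first pairs fall outside the new listing, and the SAP should say whether to show them separately. Leave the DLT criterion unchanged.

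The cost is one SAP sentence, three flag columns and possibly a few more rows. No new data are needed: protocol 7.3.1 and 7.3.2 already schedule AST, ALT, total bilirubin and ALP at the treatment visits.
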